### **2.2.4 Pharmacokinetic Endpoints**

The pharmacokinetic endpoints are as follows:

- Apparent clearance (CL) and volume of distribution (VD)
- Exposure at steady-state (AUC0-24,ss)
- Other individual exposure estimates (e.g., Cmax, Tmax, AUC for a specific time interval) may also be derived as appropriate

### **2.2.5 Safety Endpoints**

Safety will be assessed through:

- Occurrence, nature and intensity of adverse events, serious adverse events and non-serious adverse events of special interest, as determined using the Adverse Event Severity Grading Scale
- Physical and neurologic examinations, vital signs, hematology, blood chemistry and urinalyses, ECGs and C-SSRS

### **2.3 DETERMINATION OF SAMPLE SIZE**

Prior to protocol version 6, a sample size of 240 subjects with ASD (80 per treatment arm) providing evaluable data at Week 24 ensured the study 80% power to detect as statistically significant, at 1-sided 5% significance level, a difference between each active dose and placebo with an effect size of at least 0.4. For the Vineland™-II 2DC score, assuming a standard deviation of about 12.5 points, then the effect size of 0.4 corresponds to 5 points. No adjustment for multiple doses was performed. Considering a withdrawal rate of around 15-20%, it was planned to recruit approximately 300 subjects overall.

In accordance to protocol version 6, 80 subjects per treatment arm (balovaptan 10 mg equivalent and placebo) are required, for a total sample size of approximately 160 subjects with ASD with evaluable data at Week 24. To achieve this number of evaluable subjects, the overall sample size in the study since it started is expected to increase to approximately 340 subjects.

### **2.4 ANALYSIS TIMING**

The primary analysis will be conducted when the double-blind 24-week treatment period ends. Database lock will occur once all subjects have either completed the 24-week assessment or withdrawn from the study early, and all data required for analysis have been cleaned and verified.

An efficacy and safety interim analysis is planned once approximately 80 subjects taking either balovaptan 10 mg equivalent or placebo (i.e., approximately 40 subjects per treatment arm) have completed their 12-week visit without dose interruptions or adjustments to allow internal decisions for the next steps of the development plan.

Given the hypothesis generating nature of this study, the Sponsor may conduct up to two interim analyses beyond what is specified elsewhere in this protocol. The decision to conduct such an interim analysis and its timing will be documented in the Sponsor's study master file prior to the conduct of the interim analysis. The clinical study report will also document that such an interim analysis occurred. Interim analyses will be performed and interpreted by the IMC and SOC members (as appropriate), who will have full access to unblinded data.

## **3 STUDY CONDUCT**

### **3.1 RANDOMIZATION CONSIDERATIONS**

After all subjects have been randomized, the data entered into the IxRS system will be reviewed for consistency with the data entered into the Case Report Form (CRF). In

particular, the randomization dates and stratification factors (sex and age) will be checked and a summary of the discrepancies between the IxRS and CRF will be reviewed.

### **3.2 TREATMENT GROUPING**

As the starting doses in children aged between 5 and 14 years were shown to not achieve the target adult exposure, the treatment grouping originally expected - Placebo, balovaptan 4 mg equivalent and balovaptan 10 mg equivalent - is no longer tenable.

Given the numerous different dose regimens occurred in the study, as described in Table 3, the individual treatment level will be ultimately identified based on individual subject's PK exposure, estimated as the average plasma concentration ( $C_{ave}$ ) since treatment start.

$C_{ave}$  was not specifically listed in the Pharmacokinetic endpoints section of the protocol, however, in the situation of possible dose adaptations within an individual during the course of the study,  $C_{ave}$  is the PK exposure measure that reflects most realistically the individual exposure. Moreover,  $C_{ave}$  also takes into account potential dose interruptions during treatment. For subjects without dose changes or dose interruptions,  $C_{ave}$  is approximately equal to  $AUC_{0-24,ss}$  divided by 24 hrs. Individual  $C_{ave}$  will be estimated by the pharmacometrics group in Clinical Pharmacology for all subjects with at least one adequately documented PK measurement at steady-state, using a population PK modeling approach.  $C_{ave}$  at week 12 will be used as a classification factor to split the subjects receiving balovaptan into three equally sized exposure sub-groups: Low Tertile, Medium Tertile and High Tertile.

If insufficient exposure data are available for a subject and  $C_{ave}$  cannot be derived (this can happen, for example, to withdrawals or in case of issues with PK sample analyses), then his/her data will contribute to the same treatment group of the majority of his/her coetaneous taking the same regimen as per randomisation. For example, if a 6 years-old initially randomized to 1.5mg switched to 3mg and no PK data are available for him/her, then his/her data will be attributed to the Low Tertile if most of the 5-7 years-old subjects taking the same regimen are allocated, based on their available exposure, to the Low Tertile. In case no other coetaneous providing exposure data went through the same regimen pattern (as in the example, increasing dose from 1.5mg to 3mg) then data will be attributed to the same exposure sub-group of the majority of his/her coetaneous taking the same final dose (in the example, 3mg).

This treatment grouping will be used for descriptive (ie, not inferential) statistical reporting purposes of efficacy and safety data.

For pharmacometric exploratory graphical analyses, missing PK information will not be imputed. In case of missing PK information for subjects assigned to a starting dose other than Placebo, the subject with missing PK information will be excluded from exposure-efficacy analyses.

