Subjects from first adolescent and first children cohorts, who stopped treatment in the context of the interim safety and PK decisions, (see Section 3.1.3) will be allowed to re-start in the same treatment arm, according to their original randomization, for 24 weeks in the main study, provided the Investigator can exclude relevant changes in the subject's general condition (see Section 4.2.1). These subjects will have a new, abbreviated Baseline visit, and will continue with all subsequent visits according to the schedule of assessments until completion of their time on the study (Appendix 1).

In addition, re-starting subjects will be assigned a new subject number. Some data from their original screening visit will be required to be re-entered in the eCRF under the new subject number.

A screening examination will be performed approximately 4 weeks (at least 3 weeks and up to 4 weeks) before the first drug administration (Day 1) per the Schedule of Assessments, (see Appendix 1). Subjects must fulfill all entry criteria to be accepted into the study.

For subjects enrolling in first adolescent/first children cohorts (see Section 3.1 and Section 3.1.3.1), a screening examination will be performed approximately 4 weeks (at least 1 week and up to 4 weeks) before the first drug administration (Day 1) per the Schedule of Assessments (Appendix 2).

The Investigator, or designee, will use the eCRF with the assigned subject number and enter the corresponding number for allocation to the treatment group in the appropriate place on each subject's eCRF.

The randomization numbers are to be allocated sequentially in the order in which the subjects are enrolled. A Subject Enrollment and Identification Code List must be maintained by the Investigator.

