#### Baseline Definition

Unless otherwise stated, baseline is defined as the last non-missing value recorded before the first study drug administration of each repeated study drug period (ie. 8 weeks for the First Part, and 24 weeks for the Main Part) or soon after the start of the dosing (see Table above). The last observation can be an unscheduled / repeated measurement.

Baseline for Electrocardiograms (ECGs) is derived as the mean of the triplicate measurements of pre-dose assessments.

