**Table 4. Patterns of subjects' disposition**

| Pattern | Description: Subjects ...   | First Part
(Study part 1):
up to 8 weeks
of Treatment | Main Part
(Study part 2):
24 weeks of
Treatment |
|---------|---|--|--|
| a)      | stopped treatment prior to determination of final doses by IMC/SOC  |  |  |
| b)      | stopped treatment prior to determination of final doses by the IMC/SOC and took the opportunity to restart in the Main Part |  |  |
| c)      | allowed by the IMC/SOC to continue and complete the 24 weeks of treatment without dose interruption/adjustment              |  |  |
| d)      | enrolled in the Main Part   |  |  |

The primary **Efficacy** treatment comparison (balovaptan 10 mg equivalent dose vs. placebo) will be performed on the dataset obtained by pooling data from patients that were expected to take treatment for 24 weeks, as described by patterns c) and d) [highlighted in yellow].

**Safety** analysis will be performed separately on two datasets, according to the duration of the seamless treatment period that subjects have been exposed to. Therefore, two safety analysis datasets are identified:

- **First Part (8 weeks)** - Data from subjects that took treatment up to a maximum of 8 weeks, as described in pattern a) and 1st part of b) [framed with dotted red line]
- **Main Part (24 weeks)** - Data from subjects that took treatment up to a maximum of 24 weeks, as described in pattern c), d), and 2nd part of b) [framed with dotted blue line]

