#### **4.2.1         Safety Population**

- Safety Global

The “Safety Global” population consists of all subjects who gave informed consent and received at least one dose of study medication, whether prematurely withdrawn from the study or not.

Data will be summarized according to treatment classified as derived from PK exposure: Placebo, Low Tertile, Medium Tertile, High Tertile and All Treated with Active.

- Safety Inferential

The “Safety Inferential” population consists of the subset of the “Safety Global” population that is identified to address the primary efficacy study objective.

Data will be summarized according to treatment classified as: Placebo, 10mg equivalent.

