### **4.6 SAFETY ANALYSES**

Summary tables and graphs will be provided both for the “Safety Global” and for the “Safety Inferential” populations, while listings of individual data will be provided for the “Safety Global” population only, separately by subjects’ patterns (a, b, c, d).

As appropriate, listings, summary tables and graphs by treatment group will be provided for safety and tolerability assessments, including:

- Incidence of adverse events (overall, by intensity, and by relationship to study medication).

- Serious adverse events and adverse events of special interest will be reported separately.
- [REDACTED]
- Vital signs (systolic blood pressure, diastolic blood pressure, pulse rate, and orthostatic effects)
- [REDACTED]
- Physical examination (height, weight, neurological examination)
- Safety laboratory values (including hematology, blood chemistry, coagulation, and urinalysis parameters)
- Incidence of marked laboratory abnormalities
- Clinical assessment of suicidality (C-SSRS)

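### Does grouping the safety tables by Week-12 average concentration hide adverse events that interrupt dosing?

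*SAP*

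**What the plan says.** SAP Section 3.2 explains that the planned placebo, 4 mg and 10 mg grouping broke down because the starting doses missed the target exposure at ages 5 to 14. It replaces that grouping with individual exposure: Cave, counted from treatment start, which "also takes into account potential dose interruptions during treatment". The classification rests on a single time point, and the value "at week 12 will be used as a classification factor to split the subjects receiving balovaptan into three equally sized exposure sub-groups". The section then limits the use: "This treatment grouping will be used for descriptive (ie, not inferential) statistical reporting purposes of efficacy and safety data".

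Section 4.2.1 applies the tertiles to the Safety Global population, next to a placebo column and one that combines every actively treated subject.

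Section 4.1 and Table 5 (Section 4.2.2) split Safety Global into two datasets. The Main Part covers up to 24 weeks. The First Part is defined as "Data from subjects that took treatment up to a maximum of 8 weeks". Baseline is taken "before the first study drug administration of each repeated study drug period" (Section 3.3), and Protocol Section 4.6.2.1 adds that "re-starting subjects will be assigned a new subject number".

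**The concern.** Grouping by a variable that the outcome can change is a familiar trap. Time off drug lowers Cave, so a subject whose adverse event interrupts dosing before Week 12 can fall a tertile because of the very event being tabulated. If toxicity rises with exposure, a true gradient would look flatter.

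The other safety population does not fill the gap. Safety Inferential is the subset that serves the primary efficacy objective, and SAP Section 4.2.2 removes subjects with dose adjustments or interruptions from that subset.

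The second worry is the averaging window. First Part subjects are treated for at most 8 weeks, yet they are classified by a Week-12 measure. Their Cave should usually be estimable, since Protocol Section 4.6.1.8 samples them at Weeks 1, 2 and 4 and Section 1.2.2.3 puts steady state at about 7 days. The fallback rule for missing Cave would then not apply, and the SAP does not say whether their average runs to last dose or to Week 12. Subjects who stop early in the Main Part raise the same question.

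**Working it through.** The SAP gives no figure for this grouping, so there is none to reproduce. The size has to come from a model.

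**Inputs from the documents.** Approximately 340 subjects (SAP Section 2.3); Cave counted from treatment start and cut into tertiles at Week 12 (Section 3.2); Main Part tables covering 24 weeks (Section 4.1).

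**Assumptions.** Equal mix of 4 and 10 mg eq; log-normal exposure with CV 40%; true event rate either 10% in every tertile or 6/10/14%; 20%, 50% or 100% of events interrupting dosing; gaps of 1, 2 or 4 weeks. Protocol Section 5.2, which holds the interruption guidelines, is largely redacted.

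**Step 1: effect on one subject.** Cave multiplier = (12 − weeks off drug before Week 12)/12. This is 11/12 = 0.917 for 1 week, 10/12 = 0.833 for 2 weeks and 8/12 = 0.667 for 4 weeks.

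**Step 2: effect on the table.** Subjects are re-sorted into tertiles after applying the multiplier. Placing every gap wholly before Week 12 is the worst case. The Main Part table counts events over 24 weeks: an event after Week 12 cannot change Week-12 Cave, and a gap that straddles Week 12 counts only in part. The last column spreads onset uniformly over 24 weeks (also an assumption) and cuts the gap at Week 12. Onset clustered early would lie between the two columns.

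| True rate, Low/Medium/High | Events interrupting | Gap | All gaps before Week 12 | Onset uniform over 24 weeks |
|---|---|---|---|---|
| 10/10/10% | 20% | 4 weeks | 11.1/10.0/8.9% | 10.5/10.0/9.5% |
| 6/10/14% | 50% | 4 weeks | 8.9/11.0/10.0% | 7.2/10.5/12.3% |
| 6/10/14% | 100% | 2 weeks | 8.6/11.0/10.4% | 7.3/10.5/12.3% |
| 6/10/14% | 100% | 4 weeks | 11.8/12.0/6.2% | 8.4/10.8/10.8% |

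Repeat runs agree to about 0.1 point.

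**Step 3: scale.** With active:placebo between 1:1 and 2:1, the actives number 340/2 = 170 to 340 × 2/3 = 227, or 57 to 76 per tertile. The standard error of a 10% rate is √(0.1 × 0.9/57) = 4.0 points to √(0.1 × 0.9/76) = 3.4 points. With a flat 10% rate, 20% of events interrupting and all gaps early, the Low and High shifts are 0.2 to 1.3 points across gap lengths, dose mixes of 1:1 and 1:2, and CVs of 40% and 60%. In subjects, that is 0.002 × 57 = 0.1 to 0.013 × 76 = 1.0 per tertile.

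**Step 4: First Part window.** Averaging an 8-week course to Week 12 gives 56/84 = 0.667 of on-treatment exposure. With tertile cuts pooled over all actives and the same exposure mix, the split would be 55/33/12% instead of 33/33/33%. Averaging to last dose moves nobody. Equal thirds is the wrong comparator, however. These cohorts took the Table 1 starting doses (Protocol Section 4.4.2.1), which missed target exposure at ages 5 to 14. If their exposure were 0.6 to 0.7 of the pooled level (an assumption), 52 to 60% would be in Low even with averaging to last dose.

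**Step 5: re-starters.** They receive a new subject number, baseline is reset for each treatment period, and Table 5 puts the first and second parts of pattern b in separate datasets. Each record therefore has its own treatment start.

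**The case for a change.** The strongest case for a change is that the mechanism is real and no planned display of the whole Safety Global population by dose or exposure avoids it. Protocol Section 6.3.1 says safety data are analyzed as randomized, but the SAP plans no such table for that population. Among interrupted subjects the movement can be large. In a separate check (log-SD of exposure 0.4 to 0.8, about 5% of subjects interrupted), 4 weeks off drug moved 34 to 59% of them down. When interruption risk rose with exposure, at log-SD 0.6, their split went from 18/30/51% to 40/33/27%. One sentence on the averaging window would cost almost nothing.

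The mechanism stands, and so does the silence on where averaging ends. The large figures describe where a small group of interrupted subjects lands, not the event rates in the tables. They also need long gaps placed before Week 12, and no visible passage suggests that most events of any type stop dosing for weeks.

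The SAP gives its reason for leaving the randomized grouping and says openly that Cave includes interruptions. The obvious companion measure, average concentration over dosed days only, has the reverse fault: events arising off drug would be counted at on-drug exposure. Choosing between the two is a matter of display preference.

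On the window, Section 3.2 speaks of interruptions during treatment. Time after a permanent stop is not that, so averaging to last dose is the natural reading.

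**Conclusion.** No change to the plan follows. Week-12 Cave does pull some interrupting events into lower tertiles. In the 24-week all-event tables the shift is about half a percentage point or less per tertile if 20% of events interrupt dosing for up to 4 weeks and onset is uniform. It is about 1 point if every gap falls before Week 12. Both are well inside the sampling error of a single tertile.

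With uniform onset, a true 6/10/14% gradient keeps its order in every setting run except 100% interruption for 4 weeks, where Medium and High tie. If gaps cluster early, order is also lost at 50% interruption for 4 weeks and at 100% for 2 weeks. These results rest on an assumed exposure spread, interruption frequency and gap length, none of which the visible text supplies.

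The missing end point of the averaging window is a detail that an analyst would settle sensibly at last dose. It concerns First Part subjects who stopped, drawn from planned cohorts of about 24 and 30 that include placebo, and subjects who stop early in the Main Part. The primary comparison, the All Treated with Active column and the listings by disposition pattern do not depend on the tertiles.

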### 3.3 TIME-WINDOWS

Efficacy and safety analyses will be performed according to the data collected at the originally scheduled visit.

In case of deviations from the visit date scheduled as per protocol the following boundaries will be implemented to identify time-windows:

| Site Visit | Time-window (days)                | Range (days)  |
|------------|-----------------------------------|---|
| Baseline   | Before or soon after Start Dosing | Up to the 1 st day of dosing                                       |
| Week 6     | 43 ± 21                           | 23 – 64   |
| Week 12    | 85 ± 21                           | 65 – 106  |
| Week 18    | 127 ± 21                          | 107 – 148   |
| Week 24    | 169 ± 21                          | 149 – at most 21 days after last double-blind Dose and prior to OLE Screening |

For Screening, the scheduled visit will be used regardless of the actual assessment days relative to the first day of study drug.

#### Baseline Definition

Unless otherwise stated, baseline is defined as the last non-missing value recorded before the first study drug administration of each repeated study drug period (ie. 8 weeks for the First Part, and 24 weeks for the Main Part) or soon after the start of the dosing (see Table above). The last observation can be an unscheduled / repeated measurement.

Baseline for Electrocardiograms (ECGs) is derived as the mean of the triplicate measurements of pre-dose assessments.

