1.2.2.3 Pharmacokinetics

Plasma exposure of balovaptan increased in a greater than dose-proportional manner following single doses of 0.5 to 76 mg, whereas an approximately linear increase in exposure was observed after repeated dosing with 12 to 52 mg/day for 14 days. balovaptan was rapidly absorbed with a median T_{max} between 1 and 4.5 hours after administration of single doses, and between 3 to 4 hours after multiple dosing. Steady state was achieved after approximately 7 days of daily dosing. Food had no relevant effect on the pharmacokinetics of balovaptan.

Renal excretion is the major pathway of elimination (approximately 53% of the drug material recovered), with most of the drug-related material in urine being composed of metabolites. A further 30% of the administered dose was recovered in feces.

[Redacted text block]

[Redacted text block]

[Redacted text block]

[Redacted text block]

[Redacted text block]

[Redacted text block]

[Redacted text block]

[REDACTED]

[REDACTED]

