8. ADOS-2 and IQ test up to 12 months old can be accepted at screening; Wechsler Abbreviated Scale of Intelligence Scale, Second Edition (WASI-II) or Wechsler Preschool and Primary Scale of Intelligence, Fourth Edition (WPPSI-IV) intelligence test will be used at screening.
9. Alcohol test and substance use tests are mandatory at screening for adolescents. At other visits and for children, only to be performed if deemed necessary by investigator.
10. Vital signs will be done pre-dose and 3 hours post-dose. Additionally, orthostatic function will be assessed pre-dose and 3 hours post-dose at baseline/abbreviated baseline, and 3 hours post-dose at Week 6 and Week 24 or Early Withdrawal Visit.
11. Planned as off-site/home visit and can be done by a nurse, however can also be performed as clinic visits.
12. Tanner staging will be done in patients 7 years and older, but not after menarche in female patients and not after voice break in male patients.
13. Pregnancy tests will be performed in female patients after menarche only.
14. PK samples: Week 8: in the evening post-dose together with safety labs; Week 12 and Week 24: pre + 2 hours post-dose + end of visit but at least 4 hours post-dose; Early Withdrawal Visit: one at any time. Samples scheduled at least 4 hours post-dose on a clinic visit day can be taken by a nurse at home.
15. Subject and caregiver will provide feedback on palatability of study medication.
16. Subjects will be asked additional questions after completion of the PedsQL.
17. RBR and CG samples should be taken at baseline upon consent, but if missed, may be taken at any visit after.
18. For children 5–11 years old, additional questions will be asked in context of Columbia-Suicide Severity Rating Scale (C-SSRS; see Section [4.6.1.12](#)).
19. Subjects from first adolescent/first children cohorts who stopped treatment on or before Week 8 in the context of the IMC/SOC dosing decision (see [Appendix 2](#), Section [3.1.3.1](#)) will be allowed to restart for an additional 24 weeks in the main study in the same treatment arm without new randomization, provided the investigator can exclude relevant changes in patient's general condition (see Section [4.2.1](#)). These patients will have a new, abbreviated baseline visit, and will continue with all subsequent visits according to the schedule of assessments. In this abbreviated baseline visit, a single ECG should be taken.

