Dispensing of study medication		x				x				
Administration of study medication		x ^P	x	x	x	x				
PK blood samples ¹⁴			P	P, x	P			x		
Clinical genotyping ¹⁷		x								

[figure not shown]
Appendix 2
Schedule of Assessments
For First Cohorts of 24 Adolescents and 30 Children
until Confirmation of Final Doses by IMC/SOC (cont.)

[figure not shown]
	Screening ² (~4 weeks)	Baseline	Home Visit at W1	W2	W4 ²	W6 ²	Home Visit ¹¹ at W8	For Discontinuation and Stopping Treatment Only ¹⁶		
								EoT ²	FU (2 W)	FU (6 W) ²
Day	-28	1	8	15	29	43	57		14	42
Time window (days)	-28 to -7	NA	±2	±2	±2	±2	±2	NA	±2	+7
Research Biosample Repository (optional)		x					For details about week 8 visit see Appendix 1 and continue according to Appendix 1			
Vineland™-II (survey)		x 1 week ¹								
ABC		x 1 week ¹				x		x		x
RBS-R		x 1 week ¹				x		x		x
PedsQL (Family Impact Scale)		x 1 week ¹								
C-SSRS ¹⁸	x	x 1 week ¹		x	x	x		x		x
PedsQL (Core and Cognitive Scale)		P 1 week ¹								
OACIS-S		P 1 week ¹				x		x		x
OACIS-I						x		x		x

[figure not shown]
Appendix 2 Schedule of Assessments For First Cohorts of 24 Adolescents and 30 Children until Confirmation of Final Doses by IMC/SOC (cont.)

[figure not shown]
3. Triplicate ECG at baseline only.
4. Demography includes Educational Level, Diagnosis of ASD, Caregiver Information, Employment and/or school Status and Living Arrangements.
5. See protocol Section 4.6.1.7 and lab manual for more details about full and abbreviated serum chemistry.
6. At screening and Follow-Up Visit (6 weeks) glycated hemoglobin (HbA1c), thyroid stimulating hormone (TSH), and free thyroxine (T4) will be assessed. [REDACTED]
7. At Week 2 and Week 6, a single ECG 3 hours post-dose; at Week 4 a single ECG preferably pre-dose.
8. ADOS-2 and IQ test up to 12 months old can be accepted at screening; Wechsler Abbreviated Scale of Intelligence Scale, Second Edition (WASI-II) or Wechsler Preschool and Primary Scale of Intelligence, Fourth Edition (WPPSI-IV) intelligence test will be used at screening.
9. Alcohol test and substance use tests are mandatory at screening for adolescents. At other visits and for children only to be performed if deemed necessary by investigator.
10. Vital signs will be done pre-dose and additionally 3 hours post-dose at baseline, Week 2 and Week 6. Orthostatic function will be assessed 3 hours post-dose at baseline and Week 6.

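### The SAP baseline rule lets a reading taken 3 hours after the first dose serve as baseline for vital signs, and first-cohort orthostatic tests have no other scheduled baseline

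*SAP*

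**What the plan says.** Under Baseline Definition in SAP 3.3, "baseline is defined as the last non-missing value recorded before the first study drug administration of each repeated study drug period". The sentence then continues "or soon after the start of the dosing (see Table above). The last observation can be an unscheduled / repeated measurement". The Baseline row of the time-window table reads "Before or soon after Start Dosing", with a range that runs up to the first day of dosing. No hour limit is given, and nothing says that a pre-dose value takes precedence when both exist. One measure has its own rule: "Baseline for Electrocardiograms (ECGs) is derived as the mean of the triplicate measurements of pre-dose assessments". Vital signs have none.

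SAP 4.6 counts orthostatic effects among the vital signs. It plans tables by treatment group and time, both as raw values and as change from baseline.

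The Day 1 schedule differs between the two appendices:
- Protocol Appendix 1 (main study), footnote 10: vital signs are taken before and 3 hours after the dose, and "orthostatic function will be assessed pre-dose and 3 hours post-dose at baseline/abbreviated baseline, and 3 hours post-dose at Week 6 and Week 24" or at early withdrawal.
- Protocol Appendix 2 (first cohorts), footnote 10: vital signs are again taken before and 3 hours after the dose at baseline, but "Orthostatic function will be assessed 3 hours post-dose at baseline and Week 6". No pre-dose orthostatic test is listed.

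**The concern.** A reading made 3 hours after the first dose is an on-treatment observation. If it is used as baseline, any acute drug effect is already in it and is removed from every later change score in the balovaptan arm. Placebo subjects have no such effect to remove. The between-arm difference in change from baseline then moves towards zero, which for a safety table is the falsely reassuring direction. The only first-dose orthostatic reading would also be labelled baseline rather than on-treatment.

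Protocol 5.2.2 names a fall in blood pressure and impaired orthostatic function as hypothetical consequences of V1a antagonism, and this is why these measures are monitored. Two programmers could also build different tables from the same SAP text.

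**Working it through.** The documents give no figure to reproduce here. The check is a comparison of the texts, followed by simple algebra.

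**Step 1. Which Day 1 reading becomes baseline?**

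| Measure | Schedule | Pre-dose | 3 h post-dose | Literal rule | Fallback reading |
|---|---|---|---|---|---|
| ECG | Appendices 1 and 2 | yes | no | pre-dose | pre-dose |
| Supine vital signs | Appendices 1 and 2 | yes | yes | 3 h | pre-dose |
| Orthostatic | Appendix 1 | yes | yes | 3 h | pre-dose |
| Orthostatic | Appendix 2 | none scheduled | yes | 3 h | 3 h |

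The literal rule takes the last non-missing value inside the window. The fallback reading uses a post-dose value only when no pre-dose value exists. The last row is the same under both.

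**Step 2. Is drug present at 3 hours?** Protocol 1.2.2.3 gives median Tmax as "between 1 and 4.5 hours after administration of single doses, and between 3 to 4 hours after multiple dosing", so 3 hours lies inside the single-dose range. The same section says "Steady state was achieved after approximately 7 days of daily dosing". If effect follows concentration, the first dose should therefore produce only part of the later effect. I put no figure on that part, because the section also reports greater than dose-proportional exposure after single doses.

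**Step 3. Size of the distortion.** Let E be the true active-minus-placebo effect at a later visit, f the fraction of E already present 3 hours after the first dose, and p the share of the balovaptan group with a post-dose baseline. With the same mix of baselines in both arms, any non-drug change between the pre-dose and 3-hour readings cancels, and

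expected difference in change = (1 − p·f)·E.

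The documents give neither E nor f. Taking f = 0, 0.5 and 1 as assumed values:
- p = 1 (literal rule, or Appendix 2 orthostatic data): E, 0.5E, 0.
- p = 0: E throughout.

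**Step 4. What is p under the fallback reading?**

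*First Part safety dataset.* SAP Table 5 builds it from pattern a and the first period of pattern b, all on Appendix 2. For orthostatic effects, p = 1.

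*Safety Inferential.* This set pools patterns c and d, and SAP 4.2.2 removes subjects with dose adjustments or on a dose other than the final one for their age. Protocol Tables 1 and 2 show that the 10 mg-equivalent dose rose for every age from 5 to 14 (3, 5 or 7 mg to 7 or 10 mg) and stayed at 10 mg only for ages 15 to 17. First-cohort balovaptan subjects on the old doses at ages 5 to 14 therefore drop out. For the rest:
- 24 adolescents randomized 1:1:1: 24 × 2/3 = 16 on active drug.
- Protocol 4.3 reserves 10 active places for ages 13 to 14: 16 − 10 = 6 aged 15 to 17.
- Half of these on the 10 mg arm: 6/2 = 3.
- Against the planned 80 per arm: p = 3/80 = 3.75%.

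The expected difference is then (1 − 0.0375 × 0.5)E = 0.98E at f = 0.5, and 0.96E at f = 1. Protocol 4.3 allows the cohort to grow. If it doubled (assumed), p = 6/80 = 7.5%, giving 0.96E and 0.93E.

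*Safety Global, Main Part.* This also contains pattern c, at all doses. The documents do not say how many first-cohort subjects continued, so I give no share.

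**The case against.** The strongest reply is that the literal reading is not the natural one. The main clause fixes baseline before the first dose, and letting a later value override an existing pre-dose value would empty that clause. SAP 3.3 bases analyses on scheduled visits and brings in the window table only for departures from the visit date; a planned 3-hour reading is not such a departure. Protocol 4.4.2.2 has the first dose follow the pre-dose baseline assessments. I accept that the fallback reading is the more natural, and it would protect supine vital signs and all Appendix 1 data.

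Further points limit the effect. Protocol 5.2.2 says that clinical experience so far does not indicate an effect on heart rate or blood pressure, and with no first-dose effect there is no bias. The tables are descriptive, raw values by group and time are planned beside them, and an orthostatic test already contains its own supine-to-standing comparison. Most of Protocol 5.2 and some bullets in SAP 4.6 are blacked out, so other handling of blood-pressure findings cannot be excluded. The SAP baseline definition itself is not redacted.

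All of this stands, and it sets the size of the point. It does not remove it: the SAP never states the order of preference, and the Appendix 2 orthostatic gap survives the fallback reading.

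A reader might infer more: that the trial will subtract a drug effect from its safety tables, or that a real orthostatic signal would go undetected. The documents do not support either. The first depends on a reading that the main clause argues against. The second ignores the raw-value tables and adverse-event reporting. Nor can a loss of detection be quantified, because no safety test is planned and no effect size or standard deviation is given.

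**Conclusion.** The point holds as a gap in the baseline definition, and it is minor. As written, SAP 3.3 permits a 3-hour post-dose baseline for vital signs and orthostatic effects. If the post-dose clause is a fallback only, the problem is confined to orthostatic change from baseline in Appendix 2 subjects: all of the First Part safety dataset, and likely a few percent of the balovaptan arm in Safety Inferential, where the loss is at most about 4% of any true effect at the planned cohort size.

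The estimate of 3 in 80 assumes exactly 10 active subjects aged 13 to 14, an even split between the two active arms, and that all three continued without interruption. The direction, towards no difference, requires a first-dose effect in the same direction as the later effect. The documents report no indication of one. Raw-value tables, adverse-event counts, the ECG baseline and the primary Vineland-II analysis are unaffected.

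**What to change.** In SAP 3.3, beside the ECG sentence, state that baseline for vital signs, including supine and standing orthostatic readings, is the last pre-dose value of the study drug period, and that the Day 1 reading at 3 hours is an on-treatment time point. Tabulate that time point by arm. For Appendix 2 subjects with no pre-dose orthostatic test, compute no postural change from baseline; keep them in the raw postural-change tables (standing minus supine) and state their number.

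This takes a few lines of SAP text and one extra time point from data already scheduled. Appendix 2 subjects leave the orthostatic change-from-baseline table, so the First Part would have raw orthostatic displays only. Comparing a pre-dose baseline with 3-hour follow-up readings also mixes time of day into the within-arm change, but equally in both arms, so the between-arm difference remains valid.
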